7.1 Full Analysis Set

The full analysis set (FAS) includes all randomized subjects who receive at least one dose of IP. This analysis set will be used in both efficacy and safety analyses. In efficacy

analysis, subjects will be analyzed according to their randomized treatment group assignment. For safety analysis, subjects will be analyzed according to their randomized treatment group assignment except for the following case: if a subject receives a treatment that is different than the randomized treatment assignment throughout the study, then this subject will be analyzed by the treatment received.

7.2 Subgroup Analyses

Subgroup by

- Baseline background statin therapy: on statin vs not on statin
- Screening Lp(a): < 175 nmol/L vs \geq 175 nmol/L
- Baseline Lp(a): < Median vs \geq Median

8. Interim Analysis and Early Stopping Guidelines

No interim analysis is planned for this study.

9. Data Screening and Acceptance

9.1 General Principles

The objective of the data screening is to assess the quantity, quality, and statistical characteristics of the data relative to the requirements of the planned analyses.

9.2 Data Handling and Electronic Transfer of Data

The Amgen Global Study Operations-Data Management (GSO-DM) department will provide all data to be used in the planned analyses. This study will use the RAVE database.

All data collected in the eCRF will be extracted from RAVE. Protocol deviations will be transferred from eClinical. Final PK data for all randomized subjects will be transferred from statistical programming to Amgen's PKDM group. Unblinded subject and box ID randomization lists will be provided by Amgen's randomization group and the IVRS when the study stops. Details on data transfer will be provided in the Data Transfer Plan.

9.3 Handling of Missing and Incomplete Data

9.3.1 Patterns of Missing Data

Subjects may be missing specific data points for various reasons. In general, data may be missing due to a subject's early withdrawal from study, a missed visit, or non-evaluability of a data point or an endpoint at a particular point in time. In the Data Quality Review (DQR) process, queries will be made to the sites to distinguish true missing values from other unknown values (eg, due to measurement or sample

processing error). All attempts will be made to capture missing or partial data for this trial prior to the database lock.

The frequency and pattern of missing data for efficacy endpoints will be assessed through descriptive summaries of the measurements over time.

9.3.2 Handling of Incomplete Dates

Adverse event or concomitant medication with completely or partially missing dates will be queried. If after the query is resolved, the date is still incomplete with year only or year and month only, the start date will be imputed as described in [Table 1](#) below:

Table 1. Imputation Rules for Incomplete Dates

	Missing	Imputation	Exception
Start date (AE and concomitant medication)	Day	1	Default to Study Day 1 if an event starts the same year and month as Study Day 1
	Day/Month	1-Jan	Default to Study Day 1 if an event started the same year as Day 1

9.4 Detection of Bias

This study has been designed to minimize potential bias by the use of randomization of subjects into treatment groups and the use of blinding. Other factors that may bias the results of the study include:

- major protocol deviations likely to impact the analysis and interpretation of the efficacy endpoints
- subject level unblinding before primary database lock and formal unblinding

Important protocol deviations likely to impact the analysis and interpretation of the efficacy endpoints will be tabulated in the Clinical Study Report (CSR).

Any unblinding of individual subjects prior to formal unblinding of the study will be documented in the CSR. The impact of such unblinding on the results observed will be assessed. Data from subjects whose treatment assignments are unblinded prior to formal unblinding will be listed. The timing and reason for unblinding will be included in these listings.

The units for the stratification factor based on Lp(a) (final screening Lp(a) < 175 mg/dL vs \geq 175 mg/dL) was not stated correctly in the protocol, which led to the an incorrect stratification factor being used in the randomization. This may potentially bias the results as there may be an imbalance between treatment groups in the intended stratum (final

screening Lp(a) <175 nmol/L vs \geq 175 nmol/L). This potential imbalance will be explored in sensitivity analyses by adding the intended Lp(a) stratum as a baseline covariate and as a subgroup. Subgroup analysis by median baseline Lp(a) will also be performed.

Additional sensitivity analyses may be included to assess the impact of potential biases on the primary endpoint. If any sensitivity analyses are required to evaluate potential biases in the study's conclusions, then the sources of the potential biases and results of the sensitivity analyses will be documented in the CSR.

9.5 Outliers

Various methods, including univariate summaries, histograms, scatter plots, box plots, and line graphs, may be used to identify outliers in key safety and efficacy variables.

Extreme data points will be identified during the blinded review of the data prior to database lock. Such data points will be reviewed with clinical data management to ensure accuracy. The primary analyses will include outliers in the data. Sensitivity analyses may be undertaken if extreme outliers for a variable are observed.

9.6 Distributional Characteristics

Distributional assumptions for the primary and secondary co-endpoints will be assessed. If the assumptions are not met, then alternative methods will be utilized. The use of alternative methods will be fully justified in the CSR.

9.7 Validation of Statistical Analyses

Programs will be developed and maintained, and output will be verified in accordance with current risk-based quality control procedures.

Tables, figures, and listings will be produced with validated standard macro programs where standard macros can produce the specified outputs.

The production environment for statistical analyses consists of Amgen-supported versions of statistical analysis software; for example, the SAS System version 9.2 or later.

10. Statistical Methods of Analysis

10.1 General Principles

Subject disposition, demographics, baseline characteristics, and exposure to IP will be summarized by treatment group.

Summary statistics for continuous variables will include the number of subjects, mean, median, standard deviation or standard error, the 1st (Q1) and 3rd (Q3) quartiles,

minimum, and maximum. For categorical variables, the frequency and percentage will be given. No adjustments for multiplicity will be applied.

The final analysis will be conducted when all subjects have either completed all the scheduled study visits or have early terminated from the study. At that time, the database will be cleaned, processed and the database will be locked; the study will also be unblinded. Efficacy and safety analyses will be performed on the FAS.

Unless specified otherwise, the FAS will be the default analysis set in this study and data will be summarized by randomized treatment group for evolocumab and placebo. The superiority of evolocumab to placebo will be assessed for all efficacy endpoints. The primary analysis will include testing for the primary and secondary endpoints. Lp(a) data from Medpace Reference Laboratories (MRL) will be used in the primary analysis.

Methods of handling missing data for efficacy endpoints will be described throughout this section. Missing data will not be imputed for safety endpoints.

10.2 Subject Accountability

The number of subjects screened, randomized to IP, receiving IP, and completing the study will be summarized. Key study dates for the first subject enrolled, last subject enrolled and last subject's end of study will be presented. The number and percent of subjects randomized will be tabulated by the stratification factors.

Study discontinuation and IP discontinuation will be tabulated separately by reasons for discontinuation.

The number of subjects included in and excluded from each analysis set and reason for exclusion will also be summarized.

10.3 Important Protocol Deviations

Important Protocol Deviations (IPDs) categories are defined by the study team before the first subject's visit and updated during the IPD reviews throughout the study prior to database lock. These definitions of IPD categories, sub-category codes, and descriptions will be used during the course of the study.

Eligibility deviations are defined in the protocol.

10.4 Demographic and Baseline Characteristics

Demographic (ie, age, geriatric age group [< 65 , ≥ 65 and ≥ 75], sex, race, ethnicity) and baseline disease characteristics (cardiovascular medical history, laboratory parameters, and lipid-regulating medication) will be summarized by treatment group and

overall using descriptive statistics. If multiple races have been reported for a subject, the subject will be categorized as multiple race. Difference in stratum assignment between IVRS/IWRS stratum and data-derived stratum will be tabulated.

10.5 Efficacy Analyses

The following table summarizes the key efficacy analyses that will be conducted for the primary analysis.

Endpoint	Primary Analysis Method	Sensitivity Analysis
Primary Endpoint		
• Percentage change from baseline in MDS TBR at week 16	• Multivariate regression model on FAS with dependent variables percent change from baseline in MDS TBR, percent change from baseline in Lp(a), baseline MDS TBR, and baseline Lp(a).	• Primary analysis model repeated on FAS excluding FDG-PET/CT observations made after an on-study cardiovascular event • Covariate and subgroup analyses
Secondary Endpoints		
• Percentage change in Lp(a) from baseline at week 16 • Percentage change in LDL-C from baseline at week 16 • Percentage change in ApoB from baseline at week 16	• Repeated measures model on the FAS including terms for treatment group, baseline statin use stratification factor, scheduled visit, and the interaction of treatment with scheduled visit	• Multiple imputation for subjects with missing Lp(a) data
Exploratory Endpoints		
• CCI [REDACTED] [REDACTED] [REDACTED]	• Summary statistics at week 16	

10.5.1 Analyses of Primary Efficacy Endpoint

10.5.1.1 Primary Analysis of Primary Endpoint

The primary endpoint is the percentage change from baseline in MDS TBR at week 16. In order to estimate the difference in mean percentage change from baseline in MDS

TBR and to handle missing data for the primary endpoint, a multivariate regression model will be used. The response variables are percent change from baseline in MDS TBR at week 16, baseline MDS TBR, percent change from baseline in Lp(a) at weeks 8 and 16, and baseline Lp(a). Each response follows its own regression model:¹

- Percent change in MDS TBR will be regressed on treatment group and the stratification factor (on a statin, not on a statin);
- Baseline MDS TBR will be regressed on the stratification factor (on a statin, not on a statin);
- Percentage change in Lp(a) will be regressed on the treatment group, stratification factor (on a statin, not on a statin), visit, and treatment group by visit;
- Baseline Lp(a) will be regressed on the stratification factor (on a statin, not on a statin).

The variance-covariance matrix of the error terms from the response variables in the multivariate regression will be estimated. This analysis will use the FAS.

10.5.1.2 Sensitivity Analysis of Primary Endpoint

- The model specified in Section 10.5.1.1 will be repeated¹
 - by adding covariate screening Lp(a) < 175 nmol/L and \geq 175 nmol/L,
 - by subgroups specified in Section 7.2.
- FDG-PET/CT observations made after an on-study cardiovascular event will be included in the primary analysis. A sensitivity analysis excluding these observations will be conducted.

For subgroup and covariate analyses, the data-derived stratification factor will be used. Difference in stratum assignment between IXRS/IWRS stratum and data-derived stratum will be tabulated.

10.5.2 Analyses of Secondary Efficacy Endpoints

To assess the mean percent change from baseline in the secondary endpoints of Lp(a), LDL-C, and ApoB, a repeated measures linear effects mixed model will be used on the FAS to compare the efficacy of evolocumab with placebo. The model will include the treatment group, stratification factor (on a statin, not on a statin), visit, and the interaction of treatment group and visit.

¹ See section 11.

To evaluate the impact of missing Lp(a),

- A sensitivity analysis under the assumption that subjects that discontinued IP and have missing endpoint data have a mean zero percent change from baseline will be conducted using multiple imputation.
- The mixed model will be repeated using FAS with missing values imputed for subjects who discontinued IP. Missing values will be imputed using non-missing data from subjects who discontinued IP within the same treatment group, provided that there is a sufficient number of subjects in each treatment group who discontinue IP but have non-missing endpoint data.

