**Procedures:**

After subjects complete the informed consent form, they will be screened. Two screening visits (screen 1 and screen 2) will be conducted. Subjects should complete all the required tests and procedures in screen 1 and the site will confirm that the subject meets the inclusion criteria based on these procedures before the subject proceeds to the procedures in screen 2.

Screening evaluations will include complete medical and medication history; vital signs; physical examination; measurement of body weight, waist circumference, and height; and laboratory tests (fasting lipids, Lp(a), chemistry, estimated glomerular filtration rate, hemoglobin A1C, and, if applicable, serum pregnancy and follicle-stimulating hormone). FDG PET/CT will be conducted at the screen 2 visit. Subjects will receive a placebo administration with three 1.0 mL SC injections with the prefilled AI/Pen to confirm tolerance of SC administration at the screen 2 visit (considered the placebo run-in). At this time, the subject will receive instruction/training on AI/Pen use. The maximum total screening period is 56 days, including both screen 1 and screen 2.

Subjects who meet all eligibility criteria at the end of the screening period will be randomized and will return within 3 days of randomization for day 1 procedures. Those subjects receiving lipid lowering therapy (not required to participate in this study) will continue to receive the same dose of their background lipid-lowering treatment during the entire time of screening and throughout the study.

Baseline evaluations will be performed on day 1 of treatment before subjects receive the first dose of investigational product. Laboratory tests will be conducted at day 1 (fasting lipids, Lp(a), OxPL/ApoB, IL-6, hsCRP1, biomarkers, hematology, urinalysis, and Lp(a) isoform number, hematology, and urinalysis) and week 8 (fasting lipids and Lp(a)). Adverse events, serious adverse events, adverse device effects (ADE)s, disease-related events, and changes in concomitant medications will be recorded at each visit. At the end of study visit at week 16,

---

FDG-PET/CT and laboratory tests (fasting lipids, Lp(a), OxPL/ApoB, IL-6, hsCRP1, biomarkers [serum, plasma and cell], and Lp(a) isoform number) will be conducted and adverse events, serious adverse events, ADEs, disease-related events, and changes in concomitant medications will be recorded.

[figure not shown]

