The overall study design is described by a [study schema](#) at the end of this synopsis section. For a full list of study procedures, including the timing of each procedure, please refer to [Section 7](#) and the Schedule of Assessments ([Table 1](#)).

**Statistical Considerations:** The superiority of evolocumab to placebo will be assessed for all efficacy endpoints on the full analysis set (FAS), which includes all randomized subjects who receive at least one dose of IP. The primary endpoint is the percentage change from baseline in MDS TBR at week 16. Percentage change for MDS TBR will be modeled as an analysis of covariance (ANCOVA) model with the treatment group and the stratification factor in the model. FDG-PET/CT observations made after an on-study cardiovascular event will be included in the primary analysis, and a sensitivity analysis excluding these observations will be conducted. To handle missing data, the correlations between the model errors as well as baseline values of MDS TBR and Lp(a) (and on-study percent change from baseline in Lp(a)) will be modeled. Analysis of the secondary endpoints Lp(a), ApoB and LDL-C will use a repeated measures model on the FAS including terms for treatment group, stratification factors, scheduled visit, and the interaction of treatment with scheduled visit. Safety endpoints will be summarized descriptively by treatment group. For a full description of statistical analysis methods, please refer to [Section 10](#).

---

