### **5.1 Randomization/Treatment Assignment**

Subjects who meet the eligibility requirements ([Section 4.1](#)) will be randomly assigned in a 1:1 allocation ratio to 2 treatment groups (evolocumab and placebo) in a double-blind manner. Randomization will be stratified by baseline background statin therapy (on statin vs not on statin) and by screening Lp(a) (< 175 mg/dL or  $\geq$  175 mg/dL).

The randomization date is to be documented in the subject's medical record and on the enrollment CRF. Randomization numbers will be provided to the site through an IVRS/IWRS.

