#### **10.5.3 Secondary Efficacy Endpoint(s)**

Analysis of the secondary endpoints Lp(a), ApoB, and LDL-C will use a repeated measures model on the FAS including terms for treatment group, stratification factors, scheduled visit, and the interaction of treatment with scheduled visit.

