6.2 Demographics and Baseline Related Definitions

Age

Age will be calculated or collected as the subject's age in years at enrollment as recorded on the eCRF.

Baseline Lipid and Lipid-related Parameters

Baseline values for fasting lipids (total cholesterol, HDL-C, LDL-C, VLDL-C and triglycerides), ApoA1, ApoB, CRP, Lp(a) and their derived parameters (eg, ratio between them) are defined as the mean of the two most recent non-missing fasting concentrations measured through central lab prior to or on Study Day 1. If for any reason only 1 value is available, then that value will be used as the baseline.

Other Baseline Values

For HbA1c and all other variables, the baseline value is defined as the last non-missing value collected prior to or on Study Day 1.

Change (absolute change) from Baseline

The arithmetic difference between a post-baseline value and baseline for a given time point:

Change (absolute change) from baseline = (post-baseline value – baseline value)

Percent Change from Baseline

The percent change from baseline for a given variable at a given time point is defined as: $100\% \times [(\text{value at given time point} - \text{baseline value}) / \text{baseline value}]$

Baseline CHD Risk Factors

A subject will be categorized as having 2 or more CHD Risk Factors (Y/N) from the list of the modified NCEP ATP III risk factors:

- current cigarette smoking
- hypertension
- type II diabetes mellitus
- family history of premature CHD as recorded on the eCRF
- low HDL-C defined as baseline HDL-C < 40 mg/dL in men and < 50 mg/dL in women.

Baseline National Cholesterol Education Program (NCEP) Risk Categories

Risk Factor	Defining Level
High Risk: CHD or CHD Risk Equivalent	Coronary Artery Disease OR Cerebrovascular or Peripheral Vascular Disease OR Type 2 Diabetes Mellitus OR 2 or more Risk Factors (see below) AND FRS > 20% (see Appendix A for FRS calculation)
Moderately High Risk	NOT High Risk AND 2 or more Risk Factors AND FRS \geq 10% AND \leq 20%
Moderate Risk	NOT High Risk AND 2 or more Risk Factors AND FRS < 10%
Lower Risk	NOT High Risk AND 0 to 1 Risk Factor

Risk Factors for NCEP Risk Categories:

Risk factors are: current cigarette smoking, hypertension or (baseline SBP \geq 140 or DBP \geq 90 mmHg), family history of premature CHD as recorded in the eCRF form, low HDL-C cholesterol defined as baseline HDL-C < 40 mg/dL, age \geq 45 years in men or \geq 55 years in women.

Risk Classification According to ESC/EAS Guidelines

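### The secondary lipid models leave out each endpoint's own baseline; adding it would cost almost nothing and may modestly narrow the intervals.

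*SAP*

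**What the plan says.** - SAP 10.5.2, for all three secondary endpoints: "The model will include the treatment group, stratification factor (on a statin, not on a statin), visit, and the interaction" of treatment with visit. The table in SAP 10.5 has the same terms: "including terms for treatment group, baseline statin use stratification factor, scheduled visit, and the interaction of treatment with scheduled visit".
- Protocol 10.5.3 also lists no baseline term: "Analysis of the secondary endpoints Lp(a), ApoB, and LDL-C will use a repeated measures model on the FAS including terms for treatment group", then stratification factors (in the plural), visit and treatment by visit. The synopsis agrees. SAP 4.2 plans no covariate.
- The two secondary sensitivity analyses in SAP 10.5.2 both concern missing Lp(a). Neither adds baseline.
- Fasting lipids and Lp(a) are drawn at screening 1 and day 1 (protocol Table 1). SAP 6.2 defines baseline as the "mean of the two most recent non-missing fasting concentrations measured through central lab" up to Study Day 1.
- The primary model does carry a lipid baseline: "Baseline Lp(a) will be regressed on the stratification factor (on a statin, not on a statin"), as a joint response beside percent change in TBR and in Lp(a) (SAP 10.5.1.1).
- Protocol 5.1: "Randomization will be stratified by baseline background statin therapy (on statin vs not on statin) and by screening Lp(a") at 175 mg/dL. SAP section 11 explains that this unit was wrong and that the primary analysis will stratify by statin use only. The secondary models in SAP 10.5 and 10.5.2 likewise keep only statin use.

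**The concern.** Baseline is a natural covariate for a change endpoint. Here it is already collected, already defined and already used elsewhere in the SAP. Leaving it out of the secondary models has three possible consequences:

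- Intervals may be somewhat wider than the data allow.
- A chance difference between arms in baseline stays unadjusted.
- Where week-16 values are missing, the missing-at-random assumption conditions on treatment, statin use and the week-8 value, but not on baseline.

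For Lp(a) there is a further point. With the Lp(a) stratum gone, the model has no term for Lp(a) level at all.

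**Working it through.** **The plan's own figure.** The only stated power, above 90%, belongs to the primary endpoint. With 60 × 0.75 = 45 per arm, a difference of 14, an SD of 20 and two-sided 0.05 (assumed; no level is stated), power is 0.913 (normal) or 0.907 (t). It reproduces, but does not bear on this point. The documents give no SD, power or baseline correlation for any secondary endpoint.

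**Interval width with and without baseline.** Treat the week-16 contrast as a two-arm comparison with n per arm and one covariate whose within-arm correlation with percent change is r. The ratio of half-widths is

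√(1 − r²) × √(1 + 1/(2n − 4)) × t(2n − 3)/t(2n − 2).

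At n = 45 and r = 0 this is √(1 + 1/86) × 1.0002 = 1.006.

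| r (absolute value) | Ratio, n = 45 | Ratio, n = 60 |
|---|---|---|
| 0 | 1.006 | 1.004 |
| 0.1 | 1.001 | 0.999 |
| 0.2 | 0.986 | 0.984 |
| 0.3 | 0.960 | 0.958 |

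Break-even is at about 0.11 (n = 45) or 0.09 (n = 60). At r = 0.3, 45 per arm do the work of about 48.9.

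**What r might be.** An illustrative simulation used log-normal baselines (between-subject log SD 0.2 to 0.5), within-subject variation of 5% to 20%, the eligibility cut-offs of 100 and 50 mg/dL, and baseline as the mean of two values. It gave r between about −0.02 and −0.28. At 0.28 the ratio is 0.960 × 1.006 = 0.966, or 3.4% narrower. All these inputs except the cut-offs and the two-value baseline are assumptions, and the simulation does not let the percentage effect itself vary with baseline.

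**Lp(a) separately.** Stratified allocation already limits imbalance in Lp(a). A simulation assumed 60 per arm, 25% of week-16 values missing, week-8 to week-16 correlation 0.7, blocks of 4, 10% to 30% of subjects at or above 175 mg/dL and screening-to-baseline correlation 0.95. Adding baseline changed the true variance by +0.4% at r = 0, −1% to −2% at 0.2 and −3% to −5% at 0.3, with simulation error of about one percentage point. Without stratification on Lp(a) the figure at 0.3 is about −7%. The reported standard error still falls by about 1.5% at 0.2 and 3.6% at 0.3. Part of that fall removes conservatism in the planned model and is not new information.

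**Chance imbalance, LDL-C and ApoB.** The 95% range of the difference in baseline means is ±1.96 × √(2/60) = ±0.36 SD. At r = 0.2 the extreme moves the contrast by 0.36 × 0.2 = 0.07 SD. For LDL-C, with an assumed SD of percent change of 15 to 30, that is 1 to 2 percentage points, against an expected effect of 0.7 × 60 + 0.3 × 55 = 58.5 points.

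**Effect on significance.** For Lp(a), take the 28% effect in protocol 2.3 and 45 per arm. At an assumed SD of 30, power is 0.992 without baseline and 0.995 with it at r = 0.3; at an SD of 40 it is 0.907 and 0.928. For LDL-C it is essentially 1 either way.

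**The case against.** The strongest reply is that nothing is broken. Protocol and SAP agree on a valid model, type I error is held, and the choice is between two acceptable analyses. Percent change is already scaled by baseline, and averaging two baseline values dampens regression to the mean, so r may well be small. The documents give no value for it. All of this stands, and it limits the point to a suggestion.

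The 25% dropout is stated for the TBR power calculation, and lipid data may be more complete. Subjects who stop treatment continue their visits (protocol 6.2.1.2), and those who withdraw early are to complete end-of-study procedures (7.2.3). This weakens the missing-data argument but does not remove it.

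The loss of the Lp(a) stratum is disclosed and explained in SAP section 11. It is not a hidden change.

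A reader might also infer that the secondary Lp(a) result will conflict with a baseline-adjusted one from the primary model. The documents do not support that. SAP 10.5.1.1 uses its Lp(a) equations to support the TBR estimate and to handle missing TBR, and nothing says that their Lp(a) contrast will be reported.

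None of these replies shows a material drawback to adding baseline, or another place where the secondary analyses adjust for it.

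**Conclusion.** The omission is certain; the size of the benefit is not. The cost is at most about 0.6% of interval width. Over the illustrative range of r the gain runs from nil to about 4% of width, with less true gain for Lp(a). The change would also adjust for chance baseline imbalance, let the missing-at-random assumption condition on baseline, and put an Lp(a)-level term back into the Lp(a) model.

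A reader might infer that the planned comparison is biased, underpowered, or certain to lose precision. None of these follows: randomization protects the contrast, the expected lipid effects are large, and at r near zero the planned model is marginally the more precise. Larger gains would need an r above anything the documents or the illustration support. The figures rest on the assumed r, SDs, two-sided 0.05 level and missing-data rate stated above.

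**What to change.** Before unblinding:

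1. In SAP 10.5.2 and the SAP 10.5 table, add to each secondary model the continuous baseline value of the endpoint analysed (SAP 6.2 definition) and its interaction with visit.
2. Record this in SAP section 11 as a change from protocol 10.5.3.
3. Amend SAP 4.2 to match.

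The cost is two or three sentences and about one degree of freedom per visit, at weeks 8 and 16. If unblinding has already taken place, present the adjusted model as a labelled supportive analysis and keep the planned one as the main result.
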